4 STUDY VARIABLES AND ENDPOINTS

4.1 PRIMARY VARIABLE

The primary endpoint is defined as the number of incidences of treatment-emergent adverse events (TEAE) in the ABX464 treated subjects compared to placebo.

4.2 SECONDARY EFFICACY VARIABLES

The following secondary variables will be analysed:

4.2.1 Primary Efficacy Endpoint

The proportion of subjects receiving ABX464 with clinical remission according to the Total Mayo Score (TMS) at Week 8 compared to placebo. Remission excludes friability and is based on the TMS being less than or equal to two, with no individual sub-score greater than one.

4.2.2 Other Secondary Endpoints

- The change from baseline in faecal calprotectin levels at Week 4 and Week 8 compared to placebo.
- The change from screening in TMS in subjects receiving ABX464 at Week 8 compared to placebo.
- The change from baseline in Partial Mayo Score (PMS) in subjects receiving ABX464 at Week 4 and Week 8 compared to placebo.
- The proportion of subjects achieving endoscopic remission at Week 8. Endoscopic remission is defined as a Mayo endoscopic sub-score of zero.
- The proportion of subjects achieving mucosal healing at Week 8. Mucosal healing is defined as a Mayo endoscopic sub-score of less than or equal to one.
- The proportion of subjects achieving a clinical response at Week 8. Clinical response is defined
 as the reduction of at least 3 points in TMS and 30% from baseline score with a decrease of at
 least 1 point in bleeding sub-score or an absolute bleeding sub-score of 0 or 1
- The scores and changes from baseline in mental health (MH) and physical health (PH) component summary measures of the SF-36 Questionnaire at Week 4 and Week 8.
- The number of incidences of TEAEs.
- The number of incidences of TEAEs of special interest.
- The number of incidences of TEAEs leading to investigational medicinal product (IMP) discontinuation.

• The number of incidences of specific laboratory abnormalities.

The following list includes all endpoints to be assessed by Abivax. The methods for their analysis are not included in this SAP:

- The change from screening in IL-22 expression levels in serum and rectal/sigmoidal tissue at Week 8 compared to placebo.
- The change from baseline in microRNA-124 levels in whole blood (PAXgene®) and in tissue (RNA later) at Week 4 and Week 8 compared to placebo.
- The change from screening in the histopathology/infiltrate (rectal/sigmoidal biopsies) assessed by the Geboes score at Week 8 compared to placebo.
- The change from screening in rectal microbiota using taxonomic markers at Week 8 compared to placebo.

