2.4. Secondary Endpoints

The secondary endpoints of this study are:

Primary efficacy endpoint:

The proportion of subjects receiving ABX464 with clinical remission according to the Total Mayo Score
at week 8 compared to placebo. Remission exclude friability and is based on total Mayo score ≤ 2 with
no individual sub-score > 1.

Other secondary endpoints:

- The change from screening in IL-22 expression levels in serum and rectal/sigmoidal tissue at week 8 compared to placebo.
- The change from baseline in microRNA-124 levels in whole blood (PAXgene®) and in tissue (RNA later) at week 4 and week 8 compared to placebo.
- The change from baseline in fecal calprotectin levels at week 4 and week 8 compared to placebo.
- The change from screening in the histopathology/infiltrate (rectal/sigmoidal biopsies) assessed by the

Geboes score at week 8 compared to placebo.

- The change from screening in rectal microbiota using taxonomic markers at week 8 compared to placebo.
- The change from screening in Total Mayo Score in subjects receiving ABX464 at week 8 compared to placebo.
- The change from baseline in Partial Mayo Score in subjects receiving ABX464 at week 4 and week 8 compared to placebo.
- The proportion of subjects achieving endoscopic remission at week 8. Endoscopic remission is defined as a Mayo endoscopic sub-score of 0.
- The proportion of subjects achieving improvement in endoscopic appearance at week 8. Improvement of endoscopic appearance is defined as a Mayo endoscopic sub-score of ≤ 1.
- The proportion of subjects achieving a symptomatic remission at week 8. Symptomatic remission is
 defined as a total Mayo Score ≤ 2 with no individual sub-score > 1 and rectal bleeding and stool
 frequency sub-scores of 0.
- The time to UC worsening after week 8.
- The serum concentration evaluation of ABX464 and its metabolites levels.
- The scores and changes from baseline in SF-36 Questionnaire scores at week 4 and week 8.
- The number of incidences of treatment-emergent serious adverse events.
- The number of incidences of treatment-emergent adverse events of special interest.
- The number of incidences of adverse events leading to investigational product discontinuation.
- The number of incidences of specific laboratory abnormalities.

[figure not shown]

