5.3.7. Hematology and biochemistry

For hematology and biochemistry central laboratory will be used (i.e. Eurofins). All lab dosages will be done centrally except the ESR that need to be done locally. Devices will be anyway provided by Eurofins. Regarding the calprotectin sample, the site will be asked to keep samples at -80°C till the end of the study.

Each laboratory value that is outside of the normal range will be identified. The investigator will be responsible for assessing the clinical significance of laboratory abnormalities. If the investigator is uncertain about the clinical significance of a laboratory abnormality, he/she will consult with the Sponsor medical monitor. The investigator should follow any clinically significant laboratory abnormalities until resolution.

Table 1 displays the clinical laboratory parameters that must be measured.

Table 1: Laboratory Tests

HEMATOLOGY	BIOCHEMISTRY	Stools
Hemoglobin	Sodium	Faecal calprotectin
Hematocrit	Potassium	
WBC	Chloride	
Neutrophils	Calcium	
Lymphocytes	Phosphate	
Monocytes	Glucose	
Eosinophils	BUN or urea	*****
Basophils	Creatinine	
Platelet count	AST	
ESR	ALT	
	GLDH	
	Lipase	
	Alkaline phosphatase	
	gGT	
	Total bilirubin	
	Total protein	
	Albumin	
	LOH	
	CRP	

At each biochemistry time point, a tube containing the remaining serum (at least 1 mL) should be kept and stored at -20°C for potential further liver function parameters such as soluble caspase-cleaved keratin 18 (M30 Elisa) and/or miRNA22 as a marker of early hepatotoxicity.

5.3.8. miRNA modulation

ABX464 up-regulates miRNA in PBMCs, making of this micro-RNA a potentially useful biomarker for ABX464 treatment monitoring. Determination of miRNA level in whole blood and in tissue will be performed in order to assess treatment effect by comparing before and after treatment. Assays for miRNA determination and tropism test will be conducted by ACOBIOM.

Blood will be collected in PAXgene® tubes according to lab manual instructions. The rectal/sigmoidal biopsies will be stored in RNA later according to lab manual instructions.

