7.2. Premature trial discontinuation

A subject must be withdrawn at any time from the study for the following reasons:

Subject's premature trial discontinuation could occur for the following reasons:

- Investigator's decision;
- An Adverse Event or an intercurrent condition that preclude continuation of treatment;
 - o Specifically, an increase ≥ 2.0 x ULN in liver transaminases (AST/SGOT and/or ALT/SGPT), in Alkaline phosphatase or in total bilirubin should be considered a treatment discontinuation criterion
- Worsening of the UC defined as a 2-point increase from the screening MCS with 3 days of continuous rectal bleeding confirmed by flexible sigmoidoscopy with an endoscopy subscore of 2 points or higher;
- Major protocol violation;
- Subject's decision;
- · Withdrawal of consent;

A subject who prematurely exits the study for a non-drug related reason, will be replaced (i.e. an additional subject will be randomized and receive the next treatment allocation. This may or may not be the same treatment as the withdrawn subject).

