8.5. Recording AEs and SAEs

Severity of AEs will be assessed according to CTC-AE Classification Version 4.0.

Subjects will be asked to report all AEs as part of the procedures performed at each study visit. The site personnel will document all AEs in the subject's medical record. All AEs subsequently must be recorded in the appropriate eCRF sections.

The following points must be recorded for each event:

- A description of the event in medical terms, not as reported by the subject;
- · Date of onset (start date);
- Date of resolution (stop date);
- The time of onset with respect to administering the investigational product;
- The severity of the sign/symptom or clinically significant abnormal laboratory value according to CTC-AE Classification;
- The causal relationship between the investigational product and the occurrence of each AE. This
 will be assessed by each investigator using clinical judgment. Alternative causes, such as natural
 history of the underlying diseases, concomitant medications, other risk factors and the temporal
 relationship of the event to the investigational product will have to be considered. The causality of
 all AEs should be assessed by the investigator with the following question: Is there a reasonable
 possibility that the AE may have been caused by the investigational product? And answered "NO"
 (if not related) and "YES" (if related);
- Action taken regarding the investigational product:
 - o No action;
 - o Temporary discontinuation;
 - Permanent discontinuation;
 - Subject's outcome:
 - Recovered without sequelae / resolved without sequelae;
 - Recovered with sequelae / resolved with sequelae;
 - o Recovering/Resolving;
 - o On-going;
 - o Fatal (for SAEs only).

If in any one subject, the same AE occurs on several occasions, the AE in question must be documented and assessed anew each time.

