11.4 SAFETY ANALYSES

11.4.1 Adverse Events

All AEs will be classified using the version of the MedDRA coding dictionary specified in the DMP.

Events will be classified as treatment-emergent if they started or increased in severity on or after the first date and time of medication dosing at Day 0 and up to study closure or withdrawal date. If an event start date is partial, then the start day, month, year or stop date will be used to determine if the event is treatment-emergent. If the classification of the AE cannot be determined from the data available, then the event will be considered treatment-emergent.

An overall summary table will be presented for AEs occurring from baseline to the end of the study in the following categories (*Table 14.3.1.1*):

- Any adverse event;
- Any TEAE;
- Any serious adverse event (SAE);
- Any severe adverse event (Common Toxicity Criteria [CTC] grade 3 or 4);
- Death

The primary safety endpoint, the rate of all TEAEs will be compared between the treatments by stratified likelihood ratio chi-square test on a 10% one-sided significance level and presented in the same table.

TEAEs will be further classified as follows:

Severe TEAEs: Severity classified as 'severe' (Common Toxicity Criteria [CTC] grade 3 or 4) or missing.

Serious TEAEs: Serious classified as 'yes' or missing.

Drug-related TEAEs: Relationship to study drug classified as 'yes' or missing.

Serious drug-related TEAEs: Both serious and drug-related, as specified above.

TEAEs leading to study drug discontinuation: Action taken classified as 'permanent discontinuation'.

TEAEs overall and in each of the above classifications will be summarised separately for the following periods (Tables 14.3.1.2.1 and 14.3.1.2.2):

- Period 1: Adverse event occurs or worsens from first dosing to Day 56
- Period 2: Adverse event occurs after Day 56

Summaries by SOC and PT will also be presented for TEAEs in the two periods (*Tables 14.3.1.3.1.1* and 14.3.1.3.1.2). Similar tables will be presented for each of the classifications of treatment-emergent events above (*Tables 14.3.1.3.2.1* and 14.3.1.3.6.2).

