11.4.2 Laboratory Data

The following routine clinical laboratory tests will be carried out throughout the study.

- Haematology: haemoglobin, haematocrit, white blood cells (WBC), neutrophils, lymphocytes, monocytes, eosinophils, basophils, platelet count, ESR
- Biochemistry: sodium, potassium, calcium, phosphate, glucose, blood urea nitrogen (BUN)
 /urea, creatinine, aspartate transaminase (AST), alanine transaminase (ALT), GLDH, lipase,
 alkaline phosphatase, gamma-glutamyl-transferase (GGT), total bilirubin, total protein, albumin,
 lactate dehydrogenase (LDH), CRP, T3, T4, TSH
- Stools: faecal calprotectin

The absolute values of each parameter and changes from baseline will be summarised at each visit (*Tables 14.3.2.1.1 to 14.3.2.1.3*). Laboratory parameters classified as normal/ abnormal non clinically significant (NCS)/ abnormal clinically significant (CS) will be presented in a shift table showing changes from baseline to each visit for patients with at least one abnormal CS value (*Tables 14.3.2.2.1 to 14.3.2.2.3*).

If laboratory results are repeated at the same visit, the repeated result will be used in summaries (instead of the original one) provided the sample was taken within the visit window, otherwise the original result will be used. All results will be listed.

Laboratory results at unscheduled visits will be included in the listings but will not be summarised.

Pregnancy data will be listed only.

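### Specific laboratory abnormalities and TEAEs of special interest are stated endpoints with no definition and no table, and SAP 11.4.2 can leave a value at or above 2.0 x ULN out of every laboratory abnormality count

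*SAP*

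**What the plan says.** Protocol 2.4 lists "The number of incidences of treatment-emergent adverse events of special interest" among the secondary endpoints. SAP 4.2.2 repeats it as "The number of incidences of TEAEs of special interest" and adds "The number of incidences of specific laboratory abnormalities", which the protocol also lists. SAP 4.2.2 sets apart the endpoints that the sponsor will assess outside the SAP (IL-22, miR-124, Geboes score, microbiota). Neither of these two is among them, so the SAP is where their analysis belongs.

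On adverse events, SAP 11.4.1 defines five TEAE classes: severe, serious, drug-related, serious drug-related, and leading to discontinuation of study drug. It then states: "TEAEs overall and in each of the above classifications will be summarised separately for the following periods". Special interest is not one of the classes.

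On laboratory data, SAP 11.4.2 plans by-visit summaries of values and changes. It also plans a shift table by normal, abnormal not clinically significant (NCS) and abnormal CS, "showing changes from baseline to each visit for patients with at least one abnormal CS value". Results from unscheduled visits are listed but not summarised, and a repeat taken within the visit window replaces the first result. Protocol 5.3.7 leaves the CS or NCS rating to the investigator.

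Protocol 7.2 supplies a numeric liver figure, "an increase ≥ 2.0 x ULN in liver transaminases (AST/SGOT and/or ALT/SGPT", which also covers alkaline phosphatase and total bilirubin, as a criterion for stopping treatment. Protocol 5.3.7 has serum stored for possible later assays, one of them "as a marker of early hepatotoxicity".

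**The concern.** Safety is the primary objective of this trial, and liver function is the one laboratory area for which the protocol gives a numeric criterion and keeps reserve serum. Two safety counts are promised in both documents. A programmer who follows the SAP exactly has no rule for deciding what belongs in either count and no table to put it in.

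For special-interest events the gap is mainly one of missing definition. For laboratory abnormalities there is also a conflict between the documents: the SAP output that would stand in for the missing count is narrower than what Protocol 9.3 planned, and the narrowing depends on a site judgement. With 20 subjects on ABX464, a liver signal may consist of one or two subjects, so a rule that can drop a single subject from the summary matters.

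**Working it through.** **Step 1. Follow each endpoint through the SAP.** The list of tables has 29 entries under safety: 17 on adverse events, 6 on laboratory data, 1 on vital signs, 2 on ECG and 3 on exposure and medication (17 + 6 + 1 + 2 + 3 = 29).

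| | TEAEs of special interest | Specific laboratory abnormalities |
|---|---|---|
| Stated | Protocol 2.4, SAP 4.2.2 | Protocol 2.4, SAP 4.2.2 |
| Terms, parameters or cut-offs | None in the available text | None in the available text |
| Analysis text | No class in SAP 11.4.1 | Only the general rules of SAP 11.4.2 |
| Table giving the count | 0 of 29 | 0 of 29 |
| Data field | None among the items that follow "The following points must be recorded for each event" in Protocol 8.5; no column in the shell of Listing 16.2.7 | Result, unit and investigator rating in the shell of Listing 16.2.8.2; no upper limit of normal |

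**Step 2. Compare the two documents on abnormal values.** Protocol 9.3 plans, for each parameter, the number of subjects with at least one abnormal value. SAP 11.4.2 keeps only patients with at least one CS value. An NCS value is abnormal by definition, so a subject whose abnormal values are all NCS is counted under the protocol and not under the SAP. The SAP gives no reason. The shift-table shell carries no CS-only note, so the SAP's text and its shell also differ.

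**Step 3. Follow one subject.** Entry requires AST, ALT, alkaline phosphatase and total bilirubin below 1.5 x ULN (Protocol 4.2.1). Suppose ALT later reaches 2.5 x ULN (an assumed value).

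- *Rated NCS, with no CS value.* The value enters the by-visit mean and maximum in raw units and is listed. The shift table omits the subject.
- *Seen only at an unscheduled visit.* The value is listed and not summarised. Scheduled biochemistry after Day 0 falls on Days 7, 14, 28, 56 and 63 (Protocol 5.1 and 5.2.4), so there is none for 56 - 28 = 28 days of treatment.
- *Repeated within the window, with a lower repeat.* The first value leaves the summaries and stays in the listing.
- *Adverse-event route.* Protocol 8.3.1 makes a laboratory finding an adverse event when the investigator judges it clinically significant. This is the same kind of judgement that gives the CS rating, so the route is not an independent safeguard for a value rated NCS.
- *Discontinuation route.* If treatment is stopped for the value, the subject can appear as an adverse-event withdrawal in Table 14.1.2. If a TEAE with permanent discontinuation is recorded, the subject also appears in Table 14.3.1.3.6.1 or 14.3.1.3.6.2.

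In the first three cases the subject can be missing from every laboratory abnormality count, and only the last two routes recover the subject in a table.

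**Step 4. Arithmetic.** The plan's own figures (Protocol 9.4, SAP 3.5) are reproduced with n = 20 on ABX464:

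- rate 1:10: 1 - 0.9^20 = 0.878 (stated 88%)
- rate 1:20: 1 - 0.95^20 = 0.642 (stated 64%)

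The expected numbers of cases are 20 x 0.10 = 2 and 20 x 0.05 = 1.

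These are chances that an event occurs. Whether it is then counted depends on the share q of affected subjects who reach a count, and the documents give no value for q. With p the rate of occurrence, the chance of a non-zero count is 1 - (1 - pq)^20. As an illustration over the whole range of q:

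| q | 1 | 0.75 | 0.5 | 0.25 | 0 |
|---|---|---|---|---|---|
| p = 1:10 | 0.878 | 0.790 | 0.642 | 0.397 | 0 |
| p = 1:20 | 0.642 | 0.534 | 0.397 | 0.222 | 0 |

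Applying 1:10 or 1:20 to liver elevations is an assumption. The plan gives those rates for an unspecified TEAE.

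**The case against.** The best defence is that little is lost. Special-interest events are still TEAEs, so they appear in the overall and SOC/PT tables and in Listing 16.2.7. Laboratory values are summarised by visit, with the maximum by arm, and every result is listed. Three shift tables address abnormality. Protocol 9.3 itself leaves potentially clinically significant abnormalities to the investigator, so relying on that judgement is a stated approach. A subject at the Protocol 7.2 figure would ordinarily surface as an adverse-event withdrawal. An unrecorded, untreated value rated NCS would need the site to depart from that section.

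Most of this stands, and it rules out several stronger readings that a reader might infer:

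- *That the safety data go unreported.* They do not. Only the two endpoint counts are missing.
- *That there is no laboratory abnormality table.* There are shift tables. What is missing is a count of specific abnormalities or of threshold crossings.
- *That every such liver case would be lost unless rated CS.* The adverse-event and discontinuation tables can capture it. One CS value may also bring the same patient's NCS values into the shift table.
- *That special-interest events are not flagged at data capture.* The eCRF was not available. Only the absence from Protocol 8.5 and the listing shell can be shown.
- *That 88% measures missed cases.* It is the chance that a 1:10 event occurs at least once.
- *That the definitions would be chosen after unblinding.* Protocol 9 requires SAP amendments to be signed before final database lock, and SAP 9.4 places a blind data review before it. Settling these definitions is, however, not among the topics SAP 9.4 gives that meeting.

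The defence does not answer two things: the missing definitions, and the conflict between Protocol 9.3 and SAP 11.4.2. By-visit maxima in raw units, and a listing shell without the upper limit of normal, do not show how many subjects reached 2.0 x ULN.

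**Conclusion.** The point holds in a limited form. Two stated safety endpoints have no definition in the available text and no table among the 29 listed, so their counts are not produced. For special-interest events this is a missing definition with the events still tabulated elsewhere. For laboratory abnormalities it is more: the SAP narrows the count planned in Protocol 9.3, and its rules on CS rating, unscheduled results and repeats each allow a subject at or above 2.0 x ULN to be absent from every laboratory abnormality count unless captured as a TEAE or discontinuation.

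The omission is possible, not certain, and its frequency cannot be estimated from the documents. No stated power or probability is affected. The conclusion assumes that the unavailable parts of the protocol and the eCRF do not hold the missing definitions. The change should be made because it is cheap and the primary objective is safety.

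**What to change.** These changes concern reporting only and leave the clinical rule in Protocol 7.2 as it is.

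1. Reconcile SAP 11.4.2 with Protocol 9.3 by removing the CS-only restriction from the shift tables.
2. Define the laboratory endpoint and add one Safety Set table by arm, giving number (%) of subjects and number of occurrences. Count any post-baseline AST, ALT, alkaline phosphatase or total bilirubin at or above 2.0 x ULN, and any laboratory value of CTC-AE v4.0 grade 3 or higher. Derive both from central-laboratory values, whatever the CS or NCS rating. For this table, override the general rules so that unscheduled and pre-repeat results count.
3. State in the table's definition whether the Protocol 7.2 wording is read as an absolute value or as a rise from baseline. The choice matters: from an assumed baseline of 1.0 x ULN, the first reading is met at 2.0 x ULN and the second at 1.0 + 2.0 = 3.0 x ULN.
4. Fix the MedDRA preferred terms for special interest no later than the blind data review, and add one table.

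The cost is SAP wording and a little more programming for two tables. SAP 9.2 already has central-laboratory data sent to the statistics group. The upper limits of normal must be in that transfer, which is assumed here. No new samples or visits are needed.
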